#### 8.3.2. Unsolicited Adverse Events

Unsolicited AEs and their relationship to study product are recorded in the study immediately after the first product administration at Visit 02 through the one month visit that follows the last product administration. If a subject only receives the first product administration at Visit 02 but not the second or third, then the AE Reporting Period for unsolicited AEs and their relationship to study product is immediately after Visit 02 through Visit 03. If a subject only receives the first and second product administrations at Visit 02 and Visit 03, respectively, but not the third, then the AE Reporting Period for unsolicited AEs and their relationship to study product is immediately after Visit 02 and Visit 03, respectively, but not the third, then the AE Reporting Period for unsolicited AEs and their relationship to study product is immediately after Visit 04. After this period, only SAEs, new chronic medical conditions, and confirmed cases of DENV will be recorded as an AE through the last study visit. SAEs are recorded from the time the informed consent is signed (Visit 01) through the end of the study.

The severity of an adverse event (AE) is reported on the eCRF as: Grade 1 (Mild), Grade 2 (Moderate), Grade 3 (Severe), Grade 4 (Life-threatening), and Grade 5 (Death). For any subject, only the single AE that is assessed as the primary cause of death should be assigned "Grade 5" severity. Following conventions of Clinical Data Interchange Standards Consortium (CDISC), conventions the severity data will be mapped to categories of Grade 1 (Mild), Grade 2 (Moderate), Grade 3 (Severe), where any AEs reported on the eCRF as Grade 4 (Life-threatening) or Grade 5 (Death) will be coded as Grade 3 (Severe). The CDISC compliant severity grading scale will be used for all summaries and analysis for the final analysis.

Relation of an AE to the study product is defined as Definitely Related, Probably Related, Possibly Related, and Not Related. Following CDISC conventions the AE attributions will be mapped to "Related" or "Not Related", where any AEs reported on the eCRF as "Definitely, Probably and Possibly" attributions will be mapped to the "Related" category. The CDISC compliant relationship will be used for all summaries and analysis for the CSR.

AEs will be coded into Medical Dictionary for Regulatory Activities (MedDRA) system organ class and preferred terms.

Any SAEs reported before the first study product administration receipt at Visit 02 will be listed in Table 72, Table 78, Table 84, Appendix 1. All other tables and figures of unsolicited AEs will include only AEs reported following the first study product administration.

The number and proportion of subjects reporting at least one unsolicited adverse event will be summarized by MedDRA SOC and PT by study group for each study product administration and

over all study product administrations. Denominators for percentages are the number of subjects in the Safety Analysis Population who received the administration being summarized (Table 73, Table 74, Table 75 for Part A and Table 76, Table 77 for Part B, Appendix 1). For each MedDRA system organ class and preferred term a 95% CI will be presented, along with the p-value for the comparison of study groups from a Fisher's exact test for Part A and a Chi-square test for Part B (Table 64, Table 65, Table 66, Table 67 for Part A and Table 68, Table 69, Table 70, Table 71 for Part B, Appendix 1).

The following summaries for unsolicited adverse events will be presented by MedDRA system organ class, preferred term for each administration and overall administrations, for all subjects:

- Proportion of subjects reporting adverse events by severity (Table 64 through Table 78, Appendix 1);
- Proportion of subjects reporting related adverse events by severity (Table 79 through Table 84, Appendix 1);
- Proportion of subjects reporting related adverse events by dose (Table 85 through Table 89, Appendix 1);
- Number of adverse events by dose (Table 90 through Table 94, Appendix 1);
- Number and proportion of subjects experiencing adverse events above 5% frequency threshold by MedDRA SOC and PT (Table 95 Table 96, Appendix 1);
- Bar chart of the proportion of subjects reporting any adverse events by severity (Figure 49 Figure 50, Appendix 2);
- Bar chart of adverse events by severity and MedDRA SOC for SOCs reported by 5% or more of subjects (Figure 53 Figure 54, Appendix 2);
- Bar chart of adverse events by relationship to study product (Figure 51 Figure 52, Appendix 2);

Unsolicited AEs by subject will be presented in Listing 26 through Listing 28, Appendix 3.

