With regard to product administrations, maximum solicited local reactogenicity in the 7 days after administration was reported as none by 9 (20.0%) of 45 subjects, mild by 33 (73.3%) subjects, and moderate by 3 (6.7%) subjects; no severe local symptoms have been reported. Mild pain at the injection site was the most common symptom after product administration, reported by 33 (73.3%) of 45 subjects and 3 (6.7%) subjects reported mild swelling. Maximum solicited systemic reactogenicity in the 7 days after product administration was reported as none by 21 (46.7%) of 45 subjects, mild by 20 (44.4%) subjects, and moderate by 4 (8.9%) subjects; no severe systemic symptoms or fevers have been reported. Mild or moderate malaise and headache were the most common symptoms after product administration, reported by 17 (37.8%) and 15 (33.3%) subjects, respectively. Mild or moderate symptoms of myalgia (9, 20.0%), joint pain (8, 17.7%), nausea (2, 4.4%), and chills (2, 4.4%) were reported by subjects less frequently.

**Phase 2/2B Evaluation:** VRC 705 (NCT03110770) initiated in March 2017 with accrual into Part A; accrual into Part B began in July 2017. Human experience collected in this study is summarized below. At the time of this summary, data quality assurance and monitoring are ongoing, and therefore all reported data are preliminary and should not be considered final.

VRC 705 Part A: As of July 24, 2018, 90 subjects have randomized and received at least one ZIKVwt DNA vaccination IM by PharmaJet. The last vaccination was administered on October 16, 2017. There have been no SAEs related to study product reported in this part of the study. Three (3) SAEs (including: bilateral urolithiasis, bipolar disorder exacerbation, and gunshot wound resulting in death) were reported as unrelated to study product. Overall, 68 of 90 (75.6%) subjects have had one or more unsolicited AE with maximum severity being reported as mild (Grade 1) for 35 (38.9%), moderate (Grade 2) for 28 (31.1%), severe (Grade 3) for 4 (4.4%) subjects, and fatal (Grade 5) for 1 (1.1%) subject.

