## 4.5.1. Discontinuation from Receiving Study Product

Subjects who receive at least one product administration are expected to continue with planned follow-up visits until the end of the study. If the second product administration is not given, then the subject should be discontinued from the third product administration.

A subject may be discontinued from getting study product for the following reasons:

- Pregnancy;
- Grade 3 AE assessed as related to study product (except that self-limited Grade 3 solicited reactogenicity does not require discontinuation of product administrations);
- Grade 4 AE assessed as related to study product;
- Immediate hypersensitivity reaction associated with study product;
- Confirmed ZIKV infection;
- Clinically significant intercurrent illness that is not expected to resolve before the next scheduled product administration;
- Treatment with systemic glucocorticoids (e.g., prednisone or other glucocorticoid) or other immunomodulators (other than nonsteroidal anti-inflammatory drugs [NSAIDs]), with the exception that study product administration may continue per site PI discretion if the next one occurs at least 2 weeks following completion of glucocorticoid treatment; or,
• The IND Sponsor and/or PI assess that it is not in the best interest of the subject to continue receiving study product.

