# 4.6. Criteria for Pausing and Resuming the Study

The PI for each site, study team, and IND Sponsor will closely monitor and analyze study data as they become available and will make determinations regarding the presence and severity of AEs. Product administrations, new enrollments, and randomizations will be paused and the IND Sponsor will be promptly notified according to the following criteria:

- One (or more) subject experiences a Serious Adverse Event (SAE) assessed by the PI as related to study product.
- **Two** (or more) subjects experience the same **Grade 4 unsolicited AE** assessed by the PI as related to the study product.

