# **Grading the Severity of Adverse Events:**

The FDA Guidance for Industry (September 2007): "Toxicity Grading Scale for Healthy Adult and Adolescent Volunteers [Subjects] Enrolled in Preventive Vaccine Clinical Trials" is the basis for the severity grading of AEs in this protocol. Several modifications were made to the table as follows:

- "Emergency room visit" is not automatically considered a potentially life-threatening event; these words have been removed from any "grade 4' definition where they appear in the table copied from the guidance document.
- Any laboratory value shown as a "graded" value in the table that is within the institutional normal range will not be severity graded or recorded as an AE.
- Severity grading for hemoglobin decrease on the basis of the magnitude of decrease from baseline is not applicable at the grade 1 level; only absolute hemoglobin will be used to define grade 1 decrease. Increases in hemoglobin are AEs only for values above the upper limit of normal and are graded by the systemic illness clinical criteria.
- Severity grading definition for Grade 4 local reaction to injectable product (Erythema/Redness and Induration/Swelling) included added text "requiring medical attention".
- 1 X ULN was removed from the definition for PT increase.

When not otherwise specified in the table, the following guidance will be used to assign a severity grade:

Grade 1 (Mild): No effect on activities of daily living

Grade 2 (Moderate): Some interference with activity not requiring medical intervention

Grade 3 (Severe): Prevents daily activity and requires medical intervention

**Grade 4 (Potentially Life-threatening):** Hospitalization; immediate medical intervention or therapy required to prevent death.

Grade 5 (Death): Death is assigned a Grade 5 severity.

Only the single AE that is assessed as the primary cause of death should be assigned "Grade 5" severity.

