#### Table 97:Overall Summary of Adverse Events

	Grou Grou DN/ DN/ inject	o 1:4 KVwt A, 2 ions X)	Group BNA DNA injecti (N=)	2: 4 2 Wut , 4 ons	Grou 8 n DNA DNA inject	p 3: ng Vwt X) 4 X)	[Grot 4] (N=X	£	[Grou] 5] (N=X	b A A	l Part A ubjects (N=X)	All N.	Part B bjects √=X)	All Random Subjec (N=X	uized cts ()	Subjects in Screening	r
Subjects a with	u	%	, u	%	п	%	, u	%	ц ц	~ 1	, I	, n	%	u	%	u	T
																	1
At least one local solicited reactogenicity	Х	х	x	х	х	х	х	x	x	x	x	x	х	x	х	ı	1
At least one systemic solicited reactogenicity	Х	х	x	х	x	x	x	x	x	x x	x	х	х	x	х		1
At least one unsolicited adverse event	х	х	x	x	x	x	x	×	×	×	x	x	x	x	х	x	
At least one related unsolicited adverse event	Х	х	x	х	x	x	x	x	x	x	x	х	х	x	х	x	
Mild (Grade 1)	x	×	x	х	x	х	x	x	×	×	x	х	x	x	х	x	
Moderate (Grade 2)	x	×	x	х	x	x	x	x	x	×	x	x	x	x	х	x	
Severe (Grade 3)	х	х	x	х	x	х	x	x	×	×	x	х	x	x	х	х	
Not yet assessed																	
At least one severe (Grade 3) unsolicited adverse event	x	x	x	x	×	×	×	x	×	×	×	×	x	x	x	x	
Related	х	х	x	x	x	x	x	×	×	×	x	x	x	x	х	x	
Unrelated	х	х	х	X	х	x	х	х	х	x x	x	х	x	x	х	Х	
At least one serious adverse event b	х	х	х	х	х	х	х	х	x	x x	x X	х	x	x	х	х	
At least one related, serious adverse event	х	х	х	х	х	х	х	х	х	x 2	x	х	х	х	х	х	
At least one adverse event leading to early termination c	х	Х	x	x	×	x	×	x	×	x x	x	x	х	x	х	х	
At least one new onset chronic medical condition	х	х	x	х	x	х	x	x	x	x x	x	x	x	x	х		

Statistical Analysis Plan - VRC Protocol 705

	Grou mg Zl DN iniec	p 1: 4 KVwt A, 2	Group mg ZIH DNA iniect	2: 4 «Vwt ., 4	Grou 8 n ZIK DNA	p 3: ng Vwt ions	[Grou	đ	[Group		Part A Diects	All Pa	urt B ects	All Random Subiec	ized	Subiects in
	-N)	=X)	(N=)	X)	=N)	X)	K=N)	()	(X=N)	n U	=X)		X)	X=N)	er (	Screening
Subjects a with	u	%	n	%	n	%	n	%	n %	n	%	n	%	n	%	n
N = Number of subjects in the Safety Population	u															
a Subjects are counted once for each category re	gardless	of the nu	mber of e	vents.												
b A listing of Serious Adverse Events is included	d in Tab	e 99 thro	ugh Table	\$ 101.												
c As reported on the Adverse Event eCRF.																

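### The by-arm adverse event severity tables merge life-threatening and fatal events into Severe, and no planned table counts deaths or Grade 4 adverse events by arm

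*Combined protocol and SAP*

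**What the plan says.** SAP section 8.3.2 describes the severity scale on the eCRF as running from mild and moderate to "Grade 3 (Severe), Grade 4 (Life-threatening), and Grade 5 (Death". It then says that "any AEs reported on the eCRF as Grade 4 (Life-threatening) or Grade 5 (Death) will be coded as Grade 3 (Severe", citing a CDISC convention, and sets the scope: "The CDISC compliant severity grading scale will be used for all summaries and analysis for the final analysis".

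The shells follow that rule. Tables 73-84, one per study group plus the screening segment, have Mild, Moderate and Severe columns only. In Table 97 the highest severity row is "At least one severe (Grade 3) unsolicited adverse event", and there is no row for Grade 4 or for death.

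The protocol uses a finer scale. Section 5.1 grades adverse events by Appendix IV, where Grade 4 is potentially life-threatening and "Death is assigned a Grade 5 severity". Section 6.4.2 says adverse events will be tabulated by severity, with each subject counted at the maximum. Grade 4 also has a role of its own in trial conduct. Section 4.5.1 lists "Grade 4 AE assessed as related to study product" among the reasons a subject may stop receiving product, and section 4.6 pauses the study when two or more subjects "experience the same Grade 4 unsolicited AE assessed by the PI as related to the study product".

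**The concern.** Safety is a primary objective in both parts. In Part B it is explicitly a comparison with placebo, at 1200 subjects per arm. For a preventive vaccine in healthy adults and adolescents, the top of the severity scale is what a safety reader looks at first. If Grades 3, 4 and 5 share one column, two arms with the same Severe count can differ in how many of those subjects had a life-threatening event or died, and the severity tables cannot show it. The final report also could not be set directly beside the protocol's own summaries of earlier data, which report Grades 4 and 5 separately.

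**Working it through.** **Inputs.** Subjects by maximum severity of unsolicited adverse events, from protocol section 1.4 (preliminary data as of July 24, 2018), and the mapping in SAP 8.3.2.

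**The protocol's figures, reproduced**
- Part A: 35 + 28 + 4 + 0 + 1 = 68 subjects; 68/90 = 75.6%. Grade 3 is 4/90 = 4.4%. The section reports severity as "and fatal (Grade 5) for 1 (1.1%) subject", and 1/90 = 1.1%.
- Phase 1 study of the same vaccine (VRC 320): 17 + 12 + 2 + 1 = 32; 32/45 = 71.1%. Grade 3 is 2/45 = 4.4% and Grade 4 is 1/45 = 2.2%.
- Phase 1 study of the related vaccine (VRC 319): 36 + 18 + 5 + 1 = 60; 60/80 = 75.0%. Grade 3 is 5/80 = 6.3% and Grade 4 is 1/80 = 1.3%.

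**The same data under the SAP mapping** (Severe = Grade 3 + Grade 4 + Grade 5)

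| Data | Grade 3 | Grade 4 | Grade 5 | SAP Severe |
|---|---|---|---|---|
| Part A (n = 90) | 4 | 0 | 1 | 5 (5.6%) |
| VRC 320 (n = 45) | 2 | 1 | 0 | 3 (6.7%) |
| VRC 319 (n = 80) | 5 | 1 | 0 | 6 (7.5%) |

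The two Phase 1 rows only show how the mapping behaves; the SAP does not govern those studies.

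**Does another planned output restore the lost count?**
- Table 98 counts serious adverse events by system organ class, preferred term and group, and Table 97 has rows for any serious and any related serious event. Neither splits by grade or outcome. The serious-event count does not stand in for the Grade 4-5 count: protocol 1.4 reports 3 serious events in Part A, against no subject with maximum Grade 4 and 1 with Grade 5.
- The deaths listing in SAP 8.4.1 is by subject. The columns named there include neither study group nor grade, although SAP 6.1 sorts all listings by group. Tables 99 and 100 list serious events with study group, reason for seriousness, severity and outcome.
- Tables 111-113 and 115-116, the graded shift tables and Tables 169-173 keep Grade 4 by group, but for laboratory results only. SAP 8.6 limits laboratory summaries to planned parameters.
- The vital-sign shells (Tables 174-178) also stop at Severe.

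**Consistency within the report.** SAP 8.6 grades laboratory values to Grade 4 and also states that abnormal results are reported as unsolicited adverse events. One Grade 4 result on a planned parameter is therefore Grade 4 in the laboratory tables and Grade 3 in Tables 73-84.

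**The case against.** The strongest reply is that little is hidden. Grade 4 laboratory results are shown by arm. Outside the laboratory, Appendix IV defines Grade 4 mostly by hospitalization, and unplanned hospitalization, life-threatening events and death are all criteria for a serious event. So every death and nearly every clinical Grade 4 event enters the by-arm counts in Tables 97 and 98, and can be traced through Tables 99 and 100, the deaths listing and the narratives in Table 106. Non-serious moderate and severe events are listed in Tables 102 and 103, and Listings 26-28 cover all unsolicited events.

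Most of this stands, and it limits the point to presentation. It does not supply the missing number: a reader who wants deaths or Grade 4 adverse events by arm must rebuild the counts from listings.

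Three stronger readings are tempting, and the documents do not support them.
- That no table by arm shows any life-threatening grade. The graded laboratory tables do.
- That the grade used by the pause rule is lost. The mapping applies to the final analysis. SAP 6.6.1 has pause criteria identified during the study through database features and safety reviewers, and the eCRF keeps all five grades.
- That the Part A figures reveal a masked imbalance. Part A has no placebo arm, and its one death was a gunshot wound reported as unrelated. The figures only illustrate the recoding.

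**Conclusion.** The point holds as a reporting gap that should be closed. Followed as written, SAP 8.3.2 puts Grades 3, 4 and 5 in one category in Tables 73-84 and 97, and no planned table gives a by-arm count of deaths or of Grade 4 adverse events. The result is a coarser scale than the one under which the protocol collects and grades events, and it conflicts with the SAP's own laboratory tables. On the available data the effect is small in number: in Part A, one death is absorbed and Severe moves from 4 to 5 of 90. The effect in Part B cannot be sized from the documents, because section 1.4 gives no severity breakdown of unsolicited events for that part. No sample size, power or error rate is affected, nor is real-time safety monitoring. The conclusion assumes that the shells are produced as drafted. The laboratory shells carry Grade 4 by group, so the SAP's reporting structure does not itself prevent showing it.

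**What to change.** Amend SAP 8.3.2 so that adverse event summaries use the severity grade recorded on the eCRF, with the three-level mapping kept only as an additional variable. Add Grade 4 and Grade 5 columns to Tables 73-84, and add Grade 4 and death rows to Table 97. Show the eCRF grade in the adverse event listings (Tables 99-103 and Listings 26-28). Laboratory abnormalities will then carry the same grade in the adverse event and laboratory tables. The data are already collected, so the cost is one revised paragraph and a few extra columns and rows in existing shells.

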# 8.4. Deaths, Serious Adverse Events and other Significant Adverse Events

#### 8.4.1. Deaths and Serious Adverse Events

A listing of Deaths will be presented including Subject ID, Age (years), Baseline ZIKV serostatus, Adverse Event Description, SOC, PT, Adverse Event Onset Date/End Date, Last Dose Received/Days Post Dose, Reason Reported as an SAE, Relationship to Treatment, Alternate Etiology if not Related, Outcome, and Duration of Event (days).

A listing of SAEs will be presented including Subject ID, Age (years), Baseline ZIKV serostatus, Adverse Event Description, SOC, PT, Adverse Event Onset Date/End Date, Last Dose

Received/Days Post Dose, Reason Reported as an SAE, Relationship to Treatment, Alternate Etiology if not Related, Outcome, and Duration of Event (days) (Table 99 for Part A; Table 100 for Part B; Table 101 for Screening Segment, Appendix 1). The number and proportion of subjects reporting at least one SAE will be summarized by MedDRA SOC and PT for each over all administrations (Table 98, Appendix 1).

# 8.4.2. New Chronic Medical Conditions

NCMC will be recorded on the AE form through the full duration of the study. These events will be identified from the database as any event without an end date and a date of onset greater than 28 days after the last product administration or any SAE at the time of trial completion. A blinded listing will be reviewed by the Protocol Lead Medical Officer prior to database lock. A listing of NCMC will be presented including Subject ID, Age (years), Baseline ZIKV serostatus, Adverse Event Description, SOC, PT, Adverse Event Onset Date/End Date, Last Dose Received/Days Post Dose, Relationship to Treatment, Alternate Etiology if not Related, Outcome, and Duration of Event (days) (Table 104 for **Part A** and Table 105 **for Part B**, **Appendix 1**).

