In **Part A**, each subject will receive the ZIKVwt DNA vaccine administered by PharmaJet on Day 0, Week 4 and Week 8. Group 1 will receive a total dose of 4 mg split into two 0.5 mL needle-free injections, with one IM injection given into each arm. Group 2 will receive a total dose of 4 mg split into four 0.5 mL needle-free injections (using diluent to reach the full 0.5 mL volume), with one injection given IM into each arm and each leg. Group 3 will receive a total dose of 8 mg split into four 0.5 mL needle-free injections, with one injection given IM into each arm and each leg. These regimens will help us determine if the optimal regimen is to administer the full dose into one limb or to split the dose among limbs.

In **Part B**, each subject will receive the ZIKVwt DNA vaccine or placebo administered by PharmaJet on Day 0, Week 4 and Week 8. Group 4 will receive a total dose of 4 mg split into

two 0.5 mL needle-free injections, with one IM injection given into each arm and Group 5 will receive two 0.5 mL needle-free injections of placebo, with one IM injection given into each arm.

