# 5.1.1. AE Reporting Period

The following guidelines will be used to determine if an AE should be recorded in the database:

- Solicited AEs (i.e. reactogenicity parameters) will be recorded in the study database for 7 days after each product administration without the collection of their relationship to study product.
- Unsolicited AEs and their relationship to study product must be recorded in the study database immediately after the first product administration at Visit 02 through the one month visit that follows the last product administration. Therefore, the following rules apply:
  - If a subject receives all 3 study product administrations, then the AE Reporting Period for unsolicited AEs and their relationship to study product is immediately after Visit 02 through Visit 05.
  - If a subject only receives the first product administration at Visit 02 but not the second or third, then the AE Reporting Period for unsolicited AEs and their relationship to study product is immediately after Visit 02 through Visit 03.
  - If a subject receives the first and second product administrations at Visit 02 and Visit 03, respectively, but not the third, then the AE Reporting Period for unsolicited AEs and their relationship to study product is immediately after Visit 02 through Visit 04.
- Only SAEs (as defined in Section 5.2), new chronic medical conditions, and confirmed cases of DENV infection, diagnosed locally or by the PDL, are recorded as AEs through the last study visit.
- Confirmed cases of ZIKV infection are not recorded as an AE unless the infection meets the definition of a SAE. ZIKV infections must be recorded on the ZIKV Endpoints Form throughout the full duration of the study.

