# 6.2. Endpoints

# 6.2.1. Safety

Assessment of product safety will include clinical observation and monitoring of hematological and chemical parameters. Reactogenicity will be closely monitored for 7 days after each product administration and safety evaluated by clinical visits through the study duration of 32 or 96 weeks in **Part A** or **Part B**, respectively.

The following parameters will be assessed:

- Local reactogenicity signs and symptoms;
- Systemic reactogenicity signs and symptoms;
- Laboratory measures of safety;
- Adverse events;
- Serious adverse events, new chronic medical conditions, and confirmed cases of DENV; and,
- ZIKV infection events (**Part B only**).

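### The SAP screen for new chronic medical conditions cannot pick up a non-serious condition that starts between the first dose and 28 days after the last dose, so the NCMC output is an undercount.

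*Combined protocol and SAP*

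**What the plan says.** Protocol 6.2.1 names NCMCs among the safety parameters, in the item "Serious adverse events, new chronic medical conditions, and confirmed cases of DENV", and attaches no onset window.

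Protocol 5.1.1 sets two recording periods. All unsolicited AEs are recorded "immediately after the first product administration at Visit 02 through the one month visit that follows the last product administration". "Only SAEs (as defined in Section 5.2), new chronic medical conditions, and confirmed cases of DENV infection" are then the categories still recorded up to the last visit. SAP 8.3.2 repeats this: "After this period, only SAEs, new chronic medical conditions, and confirmed cases of DENV will be recorded as an AE through the last study visit".

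SAP 8.4.2 opens with "NCMC will be recorded on the AE form through the full duration of the study". It then gives the rule by which NCMCs are found in the database. The first limb is "any event without an end date and a date of onset greater than 28 days after the last product administration" and the second is "or any SAE at the time of trial completion". A blinded listing goes to the Protocol Lead Medical Officer before database lock, and the results are shown in Table 104 (Part A) and Table 105 (Part B). Table 97 has a row counting subjects with at least one new chronic condition.

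**The concern.** The screen adds an onset condition that appears in no definition or endpoint statement elsewhere. Protocol 4.4 and SAP 8.1.2 also expect sites to recognise NCMCs whenever they arise, because a new chronic condition needing ongoing management triggers an update of concomitant medications, with no timing limit. A condition that a site treats as an NCMC during the dosing period could therefore be missing from the NCMC tables.

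Safety is a primary objective of both parts. A reader of Tables 104 and 105, or of the NCMC row in Table 97, would take them as covering the whole study. Under the rule as written, their non-serious content starts only after the 28 days following the last dose, so the dosing period itself is left out.

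**Working it through.** The plan gives no figure of its own on this point. The check is to apply the rule and measure the gap it leaves.

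**Inputs**
- Dosing: Protocol 1.5 states for Part A that "each subject will receive the ZIKVwt DNA vaccine administered by PharmaJet on Day 0, Week 4 and Week 8". The same section gives the same days for Part B. Doses fall on Days 0, 28 and 56.
- Follow-up (Protocol Précis): 32 weeks in Part A, 32 × 7 = 224 days; 96 weeks in Part B, 96 × 7 = 672 days.
- Rule (SAP 8.4.2): an event is identified if (no end date AND onset day > last-dose day + 28) OR (SAE at trial completion).

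**Rule applied to example events, last dose on Day 56 (cut-off 56 + 28 = 84)**

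| Event | Limb 1 | Limb 2 | Identified? |
|---|---|---|---|
| Non-serious, unresolved, onset Day 30 | 30 > 84: no | no | No |
| Non-serious, unresolved, onset Day 84 | 84 > 84: no | no | No |
| Non-serious, unresolved, onset Day 85 | 85 > 84: yes | no | Yes |
| SAE still open at completion, onset Day 30 | 30 > 84: no | yes | Yes |

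**Length of the gap: last-dose day + 28, as a share of nominal follow-up**

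| Doses received | Gap | Part A | Part B |
|---|---|---|---|
| Three | Day 0-84 | 84/224 = 37.5% | 84/672 = 12.5% |
| Two | Day 0-56 | 56/224 = 25.0% | 56/672 = 8.3% |
| One | Day 0-28 | 28/224 = 12.5% | 28/672 = 4.2% |

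These are shares of calendar time for subjects dosed on schedule. They are not shares of events.

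**Wording of the rule.** The phrase about trial completion could belong to the SAE limb alone or to both limbs. On either reading, a non-serious condition with onset inside the gap still fails the onset condition and is not an SAE, so it stays out.

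**Where the cut-off seems to come from.** The 28 days match the point at which Protocol 5.1.1 and SAP 8.3.2 narrow recording to SAEs, NCMCs and DENV. After that point, being on the AE form largely implies membership of one of those three categories. Before it, an NCMC sits among all other AEs and needs a separate step to be found. SAP 8.4.2 describes no such step: the medical review is of the listing, and no search of earlier onsets is mentioned.

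**The case against.** Four points can fairly be made for the plan.

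1. **The rule does not keep late onsets only.** A reader who stops at the onset condition might infer that every early chronic condition is dropped. The SAE limb has no onset restriction, so serious conditions are kept whatever their start date. This stands, and it confines the gap to non-serious conditions.

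2. **The events stay in the safety analysis.** A reader might infer that early chronic illness disappears from reporting. It does not. In that period all unsolicited AEs are recorded with their relationship to product. SAP 8.3.2 plans summaries by system organ class and preferred term with 95% CIs and between-group p-values (Tables 64-71), and by severity and relationship (Tables 73-77). Protocol 5.1 requires follow-up until events resolve or are stable, and Listings 26 and 27 show outcome and resolution date. This also stands. What is missing is identification: the listing shells have a column for SAE status but none for chronic conditions, so a reader would have to reconstruct NCMCs case by case.

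3. **The screen is followed by medical review**, so being unresolved is not the final test of chronicity. That is correct, but as described the review can only judge what the screen puts in front of it.

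4. **Harm to the conclusions is not shown.** It is tempting to say that the NCMC result is biased towards no difference just where a vaccine effect is most likely. The documents give no expected timing or count of vaccine-related chronic conditions, and no NCMC test is planned. If there were an early-onset effect of vaccine, this output would understate it; without one, the result is simply an undercount.

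**Conclusion.** The point holds for non-serious conditions. As written, SAP 8.4.2 cannot identify an NCMC that is not an SAE and starts between the first dose and 28 days after the last dose. Protocol 5.1.1 and 6.2.1 and the opening sentence of SAP 8.4.2 give no basis for that restriction. Tables 104 and 105 would be undercounts. The NCMC row of Table 97 presumably would be too, on the assumption, not stated in the SAP, that it uses the same rule.

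For three on-schedule doses the gap covers the whole dosing period plus 28 days: 37.5% of Part A and 12.5% of Part B follow-up time. It is shorter for subjects who stop early. The percentages assume on-schedule dosing and nominal follow-up of 224 and 672 days. They should not be read as the proportion of NCMCs missed, which the documents do not allow anyone to estimate. The defect lies in how events already collected are identified and labelled; no safety data are lost.

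**What to change.** In SAP 8.4.2, replace the onset condition so that the screen takes every event with no end date at last contact and onset on or after the first product administration. Leave the SAE limb as it is. State that the blinded Lead Medical Officer review, already planned before lock, confirms which of the screened events are NCMCs, and that Tables 104 and 105 and the NCMC row of Table 97 use the confirmed set.

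This is a one-sentence change to the rule plus a line on the review. It needs no new data, because these AEs are already recorded with onset and resolution dates. The cost is a longer blinded listing to review. Relying on an investigator's designation of NCMC instead would require a collected field that the AE listing shells do not show, so the wider screen with medical confirmation is the safer route.
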